6.4.3 Special Handling Instructions

Females of childbearing potential should not handle or administer pomalidomide unless they are wearing gloves.

6.4.4 Record of administration

Accurate records of all study drug administration (including dispensing and dosing) will be made in the source documents. Accurate records of all prophylactic anti-thrombotic treatment compliance will also be made in the source documents.

6.4.5 Dose Modification or Interruption

Pomalidomide Dose Reductions

Dose reduction(s) will be allowed for any subject who develops a DLT during Cycle 1 or beyond Cycle 1 who develops a toxicity that, in the opinion of the Investigator, requires a dose-reduction.

For treatment interruptions during a cycle, the (28- or 21-day) schedule of each cycle will continue to be followed. Missed doses of pomalidomide are not made up.

For treatment interruptions that delay the scheduled start of a new cycle, when toxicity has resolved as required to allow the start of a new cycle (Section 6.5), the restart day of therapy becomes Day 1 of the next cycle.

The following table provides the dose reduction sequence for pomalidomide:

Table 2: Schedule of Pomalidomide Dose Reduction

	If the DLT/Toxicity occurred or recurred at --- (mg/dose/d 1-28 or d 1-21 depending on Schedule):	Reduce dose to --- (mg/dose/d 1-28 or d 1-21 depending on Schedule):
Pomalidomide	4	3
	3	2
	2	1
	1	0.5

Dosing interruptions and reductions are not permitted during Cycle 1 unless the subject experiences a DLT. Dose interruptions and reductions are permitted beyond Cycle 2. Examples of possible reasons for and extent of dose modification management are outlined in Table 3. The events listed are not all-inclusive and are based on observations pooled from studies with all compounds in the IMiD® class of drugs. Therefore, these events may occur but are not necessarily expected. The investigator may choose to modify pomalidomide dosing further downward or discontinue pomalidomide treatment for any adverse event.

Study drug may be held (up to 21 days) and subsequent dose reductions made as outlined in Table 3. If study drug needs to be held > 21 days, the patient is to be taken off study. Once a dose has been reduced, it cannot be re-escalated.

At the discretion of the Investigator, the use of G-CSF will be permitted to manage neutropenic fever or a Grade 4 neutropenia.

Table 3: Pomalidomide Dosage Modifications for cycles ≥ 2

Common Terminology Criteria (CTCAE) Version 4.0	Adverse Event	Dose Change for Pomalidomide
Allergy/Immunology	Allergic reaction/ hypersensitivity (including drug fever) Grade 2	Hold study drug until resolved to \leq Grade 1; Decrease dose by 1 dose level
Allergy/Immunology	Allergic reaction/ hypersensitivity (including drug fever) Grade 3 or 4	Discontinue Study Drug

Common Terminology Criteria (CTCAE) Version 4.0	Adverse Event	Dose Change for Pomalidomide
Blood/Bone Marrow	Neutropenia (ANC) Grade 3 with fever or 4	Day 2-14 of cycle: Hold study drug. Follow CBC weekly; If neutropenia has resolved to \leq grade 2 restart at next lower dose level until the end of the cycle. Day \geq 15 of cycle: Hold study drug for remainder of cycle. Begin next cycle at next lower dose level
Blood/Bone Marrow	Thrombocytopenia Grade 3 or 4	Day 2-14 of cycle: Hold study drug. Follow CBC weekly; If thrombocytopenia resolves to \leq grade 2 restart at next lower dose level and continue the cycle until Day 28 or Day 21 if previously reduced. Hold anticoagulation for platelet count $<$ 50,000 Day \geq 15 of cycle: Hold study drug. Begin next cycle at next lower dose. Hold anticoagulation for platelet count $<$ 50,000
Blood/Bone Marrow	Anemia Grade 3 or 4	Hold study drug and treat anemia as needed until Hgb \leq grade 2; Decrease dose by 1 dose level
Cardiac Arrhythmia	Grade 2	Hold study drug until resolved to \leq Grade 1; Decrease dose by 1 dose level
Cardiac Arrhythmia	Grade 3 or 4	Discontinue study drug
Vascular	Thrombosis/embolism Grade 2, 3 or 4	Hold study drug and anticoagulate. Resume therapy at investigator's discretion.

Common Terminology Criteria (CTCAE) Version 4.0	Adverse Event	Dose Change for Pomalidomide
Dermatology/ Skin	Rash non-desquamation Grade 3	Hold study drug until resolved to \leq Grade 1. Decrease dose by 1 dose level
Dermatology/ Skin	Rash non-desquamation Grade 4	Discontinue study drug
Dermatology/ Skin	Rash / desquamation Grade 3, 4	Discontinue study drug
	Grade 2	The dose may be modified or discontinued at the investigators discretion.
Dermatology/ Skin	Rash Erythema multiforme	Discontinue study drug
Endocrine	Elevated or Reduced Thyroid Function Test results without symptoms of hyper- or hypo-thyroidism	Confirm test results and if significant, refer for therapy; Do not alter study drug regimen
Endocrine	Elevated or Reduced Thyroid Function Test results with symptoms of hyper- or hypo-thyroidism	Hold study drug; Evaluate etiology and refer for appropriate therapy; Restart at the prior dose once symptoms have resolved and thyroid function has been stabilized with medical and/or surgical intervention
Neurology	Neuropathy cranial/motor/ sensory Grade 2 (unless baseline was grade 2)	Hold study drug; Restart at same or 1 dose level lower once event has resolved to \leq Grade 1
Neurology	Neuropathy cranial/motor/ sensory Grade 3 or recurrence of Grade 2	Hold study drug until resolved to \leq Grade 1 or baseline if baseline was grade 2; Decrease dose by 1 dose level
Neurology	Neuropathy cranial/motor/ sensory Grade 4	Discontinue study drug

Common Terminology Criteria (CTCAE) Version 4.0	Adverse Event	Dose Change for Pomalidomide
Other pomalidomide related toxicity	Grade 3 or Grade 4	Hold pomalidomide therapy; Decrease dose by 1 dose level and restart when resolved to \leq Grade 2

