6.4 Drug Administration

6.4.1 Treatment assignments

This is a Phase I non-randomized study. Eligible patients will be allocated to treatment in the order in which they sign the informed consent and that all documentation needed to confirm eligibility has been completed. A maximum of 30 subjects will be enrolled and treated with single agent pomalidomide. Starting at dose level 1 in Schedule A, the study will enroll patients in cohorts of 3, following a standard 3 +3 statistical design. (see Section 11.0).

Definition of Dose Limiting Toxicity (DLT):

Toxicity will be evaluated according to the NCI CTCAE version 4.0, (see Appendix E)

1) Non-hematologic dose limiting toxicity (DLT) is defined as any grade ≥ 3 non-hematological toxicity occurring during the first 28 days (first cycle) of treatment, with the specific exception of:

- Isolated Grade 3 elevation of liver function tests (LFTs) without associated clinical symptoms, lasting for ≤ 7 days in duration.
- Isolated Grade 3 elevation of amylase without associated clinical symptoms
- Grade 3 hypocalcemia, hypokalemia, hypomagnesemia, hyponatremia, or hypophosphatemia which responds to medical intervention.

2) Hematological dose limiting toxicity is defined as Grade ≥ 3 neutropenia with fever ≥ 38.5 , Grade 4 neutropenia lasting for ≥ 7 days in duration, or any Grade 4 anemia or thrombocytopenia occurring during the first 28 days (first cycle) of treatment.

Definition of Maximum Tolerated Dose (MTD): MTD is defined as the highest dose level in which 6 patients have been treated with less than 2 instances of DLT.

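### A permanent Cycle 1 stop for toxicity that meets no DLT criterion is counted as a non-DLT, and the Schedule B DLT window is 21 days in one section and 28 in another

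*Combined protocol and SAP*

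**What the plan says.** **Cycle 1 dosing (Section 6.4.5).** Reduction is available after a DLT: "Dose reduction(s) will be allowed for any subject who develops a DLT during Cycle 1". Without one, the rule is: "Dosing interruptions and reductions are not permitted during Cycle 1 unless the subject experiences a DLT". Permanent stopping is left to judgment, with no cycle limit in the sentence: "The investigator may choose to modify pomalidomide dosing further downward or discontinue pomalidomide treatment for any adverse event". Section 6.7 also ends treatment for adverse events that the investigator judges too harmful to continue.

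**Table 3 (Section 6.4.5).** The title is "Pomalidomide Dosage Modifications for cycles ≥ 2", and the table is introduced with "Examples of possible reasons for and extent of dose modification management are outlined in Table 3". Six rows direct discontinuation. One of them, "Rash Erythema multiforme", carries no grade. The Grade 2 entry that follows the desquamating-rash row reads "The dose may be modified or discontinued at the investigators discretion".

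**DLT definitions.** Section 6.4.1 counts Grade 3 or higher "non-hematological toxicity occurring during the first 28 days (first cycle) of treatment", with listed laboratory exceptions. Its hematologic part covers Grade 3 or higher neutropenia with fever, Grade 4 neutropenia persisting at least 7 days, and Grade 4 anemia or thrombocytopenia. Section 11.1 repeats most of this, but sets the first cycle at 28 days on Schedule A and 21 days on Schedule B. Neither section makes discontinuation for toxicity a criterion.

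**Counting.** Section 11.2 puts every dosed patient in the MTD determination, except those who left before finishing Cycle 1 for a reason unrelated to toxicity. Section 11.1 escalates on 0 DLTs in 3 or 1 in 6. The MTD is the highest level with six patients treated and fewer than two DLTs.

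**The concern.** Cycle 1 is the DLT window, and tolerability of each dose is what the primary endpoint assesses. If toxicity forces a patient off drug for good in that window, the dose was not tolerable for that patient. Under the rules as written, the patient still fills one of the three or six places and adds nothing to the DLT count. The error runs one way, toward escalation. At dose level 1 it also helps keep Schedule A open, because abandoning that schedule requires two DLTs.

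The Cycle 1 bar on holds and reductions makes such stops more plausible. From Cycle 2, Table 3 handles Grade 3 anemia or thrombocytopenia by holding and reducing. In Cycle 1 neither event is a DLT, so the text leaves full dose or a stop. Cytopenia is a realistic route: Section 4.1 says the lenalidomide study in this disease was halted for anemia and thrombocytopenia.

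The two window lengths are a separate problem. On Schedule B the same event can be a DLT under one section and not under the other.

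**Working it through.** **1. How a non-DLT toxicity stop is scored.** Take a patient stopped permanently on day 12 for Grade 3 thrombocytopenia.
- Section 11.2: the reason is toxicity, so the exclusion does not apply and the patient stays in the denominator.
- Sections 6.4.1 and 11.1: only Grade 4 thrombocytopenia is a DLT, so the numerator is unchanged.
- Section 11.1: if neither of the other two patients has a DLT, the cohort reads 0 of 3 and the dose goes up. Had the stop counted, it would read 1 of 3 and three more patients would be treated at that level.

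No minimum Cycle 1 exposure or replacement rule changes this result. Grade 2 desquamating rash and erythema multiforme below Grade 3 follow the same path.

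**2. Table 3's discontinuation rows against the DLT definition.**

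| Row | Already a DLT in Cycle 1? |
|---|---|
| Hypersensitivity, Grade 3-4 | Yes |
| Arrhythmia, Grade 3-4 | Yes |
| Non-desquamating rash, Grade 4 | Yes |
| Desquamating rash, Grade 3-4 | Yes |
| Neuropathy, Grade 4 | Yes |
| Erythema multiforme, no grade | Only at Grade 3 or higher |

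The five graded rows are non-hematologic, Grade 3 or higher, and outside the listed exceptions. Extending Table 3 to Cycle 1 therefore does not alter their DLT count. What it alters is management: in Cycle 1 the text allows reduction after these events, whereas from Cycle 2 the table says to stop.

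**3. Schedule B window.** A Grade 3 non-hematologic event on day 25 is a DLT under 6.4.1 (28 days) and not under 11.1 (21 days). The conflict covers days 22 to 28.

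**4. The plan's own figure.** Section 11.6 gives up to 30 dose-finding patients. Six at Schedule A level 1 plus four Schedule B levels of six is 6 + 4 × 6 = 30, so the figure reproduces.

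**5. Size.** Let p be the per-patient DLT probability. The chance of escalating at a level is

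E(p) = (1 − p)³ + 3p(1 − p)² × (1 − p)³.

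Let s be the probability of a permanent Cycle 1 toxicity stop with no DLT. By definition this excludes a DLT, so if stops count the per-patient probability becomes r = p + s. Both p and s are assumptions, since the documents give neither. For p = 0.20 and s = 0.05:
- E(0.20) = 0.512 + 0.197 = 0.709
- E(0.25) = 0.422 + 0.178 = 0.600
- Fall: 10.9 points

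| p | E(p) as written | E(p + 0.01) | Fall (points) | E(p + 0.05) | Fall (points) |
|---|---|---|---|---|---|
| 0.10 | 0.906 | 0.889 | 1.7 | 0.814 | 9.2 |
| 0.20 | 0.709 | 0.687 | 2.2 | 0.600 | 10.9 |
| 0.33 | 0.434 | 0.415 | 1.9 | 0.343 | 9.2 |

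Falls are taken from unrounded values. The chance of at least one such stop among six patients is 1 − 0.99⁶ = 0.059 at 1% and 1 − 0.95⁶ = 0.265 at 5%.

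**The case against.** A grade-based DLT definition is a legitimate choice, and leaving out Grade 3 anemia and thrombocytopenia looks deliberate: patients with heavy marrow infiltration may enter with platelets as low as 20 K/µL. Tying DLT status to stopping brings in attribution and discretion that the non-hematologic definition does not now use. No sentence states that a stopped patient tolerated the dose; the scoring follows from reading 11.2, the DLT lists and the 3+3 rule together. How often erythema multiforme falls below Grade 3 depends on CTCAE v4.0, which is cited but not reproduced. The 30-day safety assessment may catch a later DLT, and six further patients are treated at the MTD.

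Most of this stands as a limit on size. It does not remove the gap. Excluding a cytopenia grade from the DLT list does not settle how to count a patient whom it takes off drug for good. The later assessment does not rescore the stop, and the six further patients come after the MTD is chosen.

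Three stronger readings are tempting and are not supported:
- **Investigators must continue or rechallenge after a severe Cycle 1 reaction.** Reduction is permitted, not directed, and 6.4.5 and 6.7 already allow a stop.
- **Table 3's title hides severe events from the DLT count.** The five graded rows are DLTs already; the only exception is days 22 to 28 of Schedule B under 11.1.
- **The sentence on modifying further downward contradicts the Cycle 1 bar.** It follows the introduction to Table 3 and can be read as going lower than that table prescribes.

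**Conclusion.** The point holds as a gap in scoring. A permanent Cycle 1 stop for a toxicity that meets no DLT criterion stays in the MTD denominator as a non-DLT and favors escalation. The effect is about 2 points on the chance of escalating at a level if 1% of patients have such a stop, and about 9 to 11 points if 5% do. Those rates are assumed, so the figures show scale and are not estimates for this trial. A reader might infer that the MTD is likely to be wrong; the documents do not support that, because they give no rate and the event is probably uncommon.

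The 21- versus 28-day conflict is certain on the text but matters only if Schedule B opens. The scope of Table 3 is a modest safety clarification. Taken together, these are worth considering for an amendment, with medium confidence.

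**What to change.** One amendment with three changes:

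- **Sections 6.4.1 and 11.1.** Add to both DLT definitions: *Drug-related toxicity that leads to permanent discontinuation of pomalidomide during the first 28 days is a DLT; the decision to discontinue must itself be made within those 28 days.* The second clause stops a Cycle 1 toxicity that leads to a stop months later from becoming a DLT after escalation has been decided.
- **Section 11.1.** Use the 28-day window for both schedules.
- **Section 6.4.5.** State that Table 3's discontinuation rows also apply in Cycle 1, so that reduction after a Cycle 1 DLT is limited to events outside those rows.

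The cost is a few sentences and a slightly more conservative DLT count that depends partly on attribution and on the investigator's decision to stop. At the assumed rates, the loss in the chance of escalating is the 1.7 to 10.9 points shown in the table. The restriction to drug-related toxicity is meant to keep out cytopenias due to the disease. Each level still takes at most six dose-finding patients, and the maximum of 30 and the 3+3 rules are unchanged.

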6.2.1 Inclusion Criteria

Subjects must meet the following inclusion/exclusion criteria to be eligible for the study.

Inclusion criteria

1. Understand and voluntarily sign an informed consent form.
2. Age ≥ 18 years at the time of signing the informed consent form.
3. Able to adhere to the study visit schedule and other protocol requirements.
4. Waldenström's Macroglobulinemia that has relapsed and/or is refractory to at least one prior line of therapy
5. All previous cancer therapy, including radiation, hormonal therapy and surgery, must have been discontinued at least 4 weeks prior to treatment in this study.
6. ECOG performance status of ≤ 2 at study entry (see Appendix D).
7. Laboratory test results within these ranges:
 - Serum creatinine ≤ 2.0 mg/dL
 - Creatinine clearance ≥ 45 ml/min
 - Total bilirubin $\leq 3 \times$ Upper Limit of Normal (ULN) or Direct Bilirubin $\leq 2 \times$ ULN
 - AST (SGOT) and ALT (SGPT) $\leq 2 \times$ ULN
 - Platelet count ≥ 20 K/ μ L
 - Absolute neutrophil count ≥ 500 K/ μ L
8. Disease free of prior malignancies for ≥ 5 years with exception of currently treated basal cell, squamous cell carcinoma of the skin, or carcinoma *“in situ”* of the cervix or breast.
9. Females of childbearing potential (FCBP)[†] must have a negative serum or urine pregnancy test with a sensitivity of at least 25 mIU/mL within 10 – 14 days prior to

[†] A female of childbearing potential is a sexually mature woman who: 1) has not undergone a hysterectomy or bilateral oophorectomy; or 2) has not been naturally postmenopausal for at least 24 consecutive months (i.e., has had menses at any time in the preceding 24 consecutive months).

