6.2.2 Exclusion criteria

1. Any serious medical condition, laboratory abnormality, or psychiatric illness that would prevent the subject from signing the informed consent form.
2. Pregnant or breast feeding females. (Lactating females must agree not to breast feed while taking pomalidomide or for 28 days after stopping pomalidomide).
3. Any medical or psychiatric condition, including the presence of laboratory abnormalities, which places the subject at unacceptable risk if he/she were to participate in the study, or confounds the ability to interpret data from the study.
4. Use of any other experimental drug or therapy within 28 days of the first dose of study drug.
5. Known hypersensitivity to thalidomide or lenalidomide.
6. The development of erythema nodosum if characterized by a desquamating rash while taking thalidomide or similar drugs.
7. Any prior use of pomalidomide.
8. Concurrent use of other anti-cancer agents or treatments.
9. Known positive for HIV or acute hepatitis A or acute or chronic active hepatitis B or C.
10. Grade >2 peripheral neuropathy

11. Neutrophil count <1000K/ μ L and/or platelet count <100K/ μ L unless infiltration by Waldenström's Macroglobulinemia equals or exceed 60% of bone marrow cellularity.

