6.5 Instructions for initiation of a New Cycle

A new course of treatment may begin on the scheduled Day 1 of a new cycle if:

- The ANC is $\geq 1.0K/\mu L$, or \geq the baseline ANC, if the baseline ANC was $<1.0K/\mu L$.
- The platelet count is $\geq 100K/\mu L$, or \geq the baseline platelet count, if the baseline platelet count was less than $100K/\mu L$.
- Any drug-related rash, neuropathy or cardiac event that may have occurred has resolved to \leq grade 1 severity or baseline.
- Any other drug-related adverse events that may have occurred have resolved to \leq grade 2 severity.

If these conditions are not met on Day 1 of a new cycle, the subject will be evaluated weekly and a new cycle of treatment will not be initiated until the toxicity has resolved as described above. A maximum delay of 21 days is allowed for any given cycle. If these conditions remain unmet on Day 21, the patient is to be taken off of the protocol.

If anti-thrombotic prophylaxis (aspirin, else warfarin or low molecular weight heparin) was held during a given cycle for a platelet count $<50 K/\mu L$, it should be resumed as soon as the platelet count recovers to $\geq 50 K/\mu L$.

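### For patients who enter with platelets of about 20 to <50 K, Section 6.5 clears a new cycle at the baseline count while Table 3 holds drug at that same unchanged count from Day 2; the two need reconciling

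*Combined protocol and SAP*

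**What the plan says.** - **Entry.** Section 6.2.1, inclusion 7, sets the floor at "Platelet count ≥ 20 K" per µL. Section 6.2.2, exclusion 11, bars counts under 100 K/µL, but waives that bar when "infiltration by Waldenström's Macroglobulinemia equals or exceed 60% of bone marrow cellularity".
- **Starting a cycle.** Section 6.5 requires at least 100 K/µL, or at least "the baseline platelet count, if the baseline platelet count was less than" 100 K/µL.
- **During a cycle, from Cycle 2.** The platelet row of Table 3 (Section 6.4.5) is triggered by "Thrombocytopenia Grade 3 or 4". For Days 2-14 the instruction is to hold drug, then "Follow CBC weekly; If thrombocytopenia resolves to" Grade 2 or better, restart one dose level lower. From Day 15 it is to hold and begin the next cycle at the next lower dose.
- **Limits.** Section 6.4.5 says "If study drug needs to be held > 21 days, the patient is to be taken off study". It also rules out going back up after a reduction.
- **Baseline allowances elsewhere.** Table 3's neuropathy rows make an exception for patients who entered at Grade 2. The platelet row has none.

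**The concern.** The protocol deliberately admits patients whose platelets are low because of marrow disease, and Section 6.5 recognises this. The platelet row of Table 3 does not. The same unchanged count can satisfy the rule on Day 1 and breach it on Day 2, and the condition for restarting within the cycle is then a count better than the patient's own baseline. Two investigators could treat the same patient differently, each with the protocol's support.

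The secondary results are at stake. Holds, dose reductions or withdrawals that reflect the disease at entry could be reported alongside drug toxicity. A patient who leaves in Cycle 2 has already completed the one cycle needed for the efficacy set (Section 11.2), but has less time on drug in which to respond.

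**Working it through.** The plan gives no figure to reproduce. The check is which entry counts meet both rules, and how long a literal hold would last.

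**1. Entry counts affected.** The documents cite CTCAE v4.0 without printing its cut-offs. I assume Grade 4 is below 25 K, Grade 3 is 25 to <50 K, and 50 K or more is Grade 2 or milder.

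| Unchanged baseline count | Section 6.5, Day 1 | Table 3, Day 2 onward |
|---|---|---|
| 20 to <50 K | may start | Grade 3-4: hold |
| 50 to <100 K | may start | Grade 1-2: no hold |

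The conflict is therefore confined to baselines of 20 to <50 K. In that band an unchanged count never reaches Grade 2.

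**2. Length of a hold.** Section 6.4.5 keeps the cycle calendar running during an interruption, so on the 28-day schedule:

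days held before the next Day 1 = 28 − trigger day + 1

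| Trigger day | Days held | More than 21? |
|---|---|---|
| 2 | 28 − 2 + 1 = 27 | yes |
| 7 | 28 − 7 + 1 = 22 | yes |
| 8 | 28 − 8 + 1 = 21 | no |
| 14 | 28 − 14 + 1 = 15 | no |
| 15 | 28 − 15 + 1 = 14 | no |

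The limit is passed before the next cycle only for triggers on Days 2-7. From Day 8, Section 6.5 can clear the next cycle at the baseline count. On Schedule B, a hold counted in missed dosing days is at most 21 − 2 + 1 = 20, so the limit is never passed; counted in calendar days, the result matches Schedule A. The protocol does not say which count applies.

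**3. What follows for later triggers.** From Day 15, Table 3 explicitly starts the next cycle at a lower dose. For Days 8-14 without recovery it does not state the dose for the next cycle; following the row implies the lower one. Because re-escalation is barred, the reduction is permanent, and it could recur in later cycles. Table 2 ends at 0.5 mg: four steps from 4 mg (4 to 3 to 2 to 1 to 0.5), and one step from 1 mg.

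**4. Whether a count would be seen.** Section 2, footnote 3, places the routine count within 5 days before Day 1 of each cycle. That count is the one Section 6.5 governs. Table 3's weekly counts begin only once drug is held. A trigger on Days 2-7 therefore needs an unscheduled count, or the pre-cycle value carried into Day 2.

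**The case against.** The strongest reply is that Table 3 is not automatic. Section 6.4.5 introduces it as examples, ties reductions after Cycle 1 to a toxicity that the investigator judges to need one, and heads the column as adverse events. An unchanged entry count is arguably none of these. This stands in part: it makes the outcome possible rather than certain. It does not remove the conflict. The same section says holds and reductions follow Table 3, the discretion it spells out is to reduce further or discontinue, and the platelet row has no test of attribution or change from baseline.

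Three stronger readings are tempting, and the documents do not support them.

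- **Every such patient is removed.** Removal needs an early trigger and a hold longer than 21 days, and no routine count falls in that window.
- **An affected patient has no chance of a confirmed response.** Section 8 requires confirmation at 6 weeks only for partial and complete responses; a minor response needs none. Section 6.4.5 also says interruptions are permitted beyond Cycle 2, whereas Table 3 covers Cycle 2 onward. If the first hold falls on Cycle 3 Day 2 (study Day 56 + 2 = 58), the 22nd held day is study Day 79. On Section 8's assessment after every cycle, a response seen at about Day 28 could be confirmed from Day 28 + 42 = 70. Nor can a share of the efficacy set lost to the rule be calculated, since the number of patients in the band is not given.
- **The neutrophil and anemia rows conflict in the same way.** The neutrophil row needs Grade 4, or Grade 3 with fever. If the intended entry floor is 500/µL and Grade 4 lies below that (both assumed), an unchanged afebrile entry count triggers nothing. For anemia, Section 6.5 has no hemoglobin baseline clause to contradict.

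It is also fair to say that Section 7.2 already has the investigator record each event's relationship to drug and the action taken, so the data for separating these cases should exist.

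**Conclusion.** The inconsistency is real and narrow. For baseline platelets of 20 to <50 K, on the assumed Grade 3 boundary of 50 K, Section 6.5 accepts a count that the Table 3 platelet row, read literally, holds. A patient with no platelet fall could have a permanent dose reduction or, with a trigger on about Days 2-7 and a hold beyond 21 days, be taken off study. Both depend on a count being acted on within the cycle and on Table 3 being applied as a rule rather than as an example.

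The number of affected patients cannot be derived from the documents, so no size of bias is given. The exposure is limited to the secondary safety and best-response summaries. The MTD rests on DLTs in Cycle 1, and Table 3 is titled for Cycle 2 onward, so the dose-finding result is untouched by this point.

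**What to change.** Reconcile the platelet row of Table 3 and the 21-day limit in Section 6.4.5 with the baseline clause in Section 6.5, so that one stated rule covers patients who enter with counts already at that grade, on Day 1 and through the cycle. Which clinical rule applies is for the investigator and sponsor to decide; none is proposed here.

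In the analysis plan in Section 11, add a listing of holds, dose reductions and removals that occur at a platelet count no lower than baseline, separate from those for toxicity.

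The cost is a wording amendment and one listing, with no extra patients or tests.

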6.4.2 Dosing regimen

There are four predefined dose levels (1, 2, 3, and 4) for pomalidomide, and two alternative dosing schedules (A and B). With schedule A, patients will be treated with the study drug for 28 days within each cycle. With schedule B, patients will be treated for 21 days within each 28 day cycle. Schedule B will only be explored if the MTD is exceeded at dose level 1 within Schedule A. The first cohort of 3 patients will be treated at dose level 1 with schedule A (28-day dosing). If no dose limiting toxicities (DLTs) are observed then the next cohort of 3 patients will be treated at next higher dose level. If one DLT is observed then 3 more patients will be treated at the same dose level. At anytime if 2 or more DLTs are observed within 3 or 6 patients at dose level 1, then schedule A is considered too toxic and will be abandoned. Patient enrollment will then be resumed using dose level 1 of dosing schedule B (21-day dosing) to determine the MTD. The purpose of schedule B is to prepare for the scenario that dosing schedule A is not tolerable.

Table 1

	Dosing Schedule A	Dosing Schedule B
Dose level 1	1 mg orally on days 1-28	1 mg orally on days 1-21
Dose level 2	2 mg orally on days 1-28	2 mg orally on days 1-21
Dose level 3	3 mg orally on days 1-28	3 mg orally on days 1-21
Dose level 4	4 mg orally on days 1-28	4 mg orally on days 1-21

Dose escalation will continue in 1 mg increments until the MTD is reached. Once the MTD has been determined, an additional 6 patients will be treated at this dose level.

An additional 6 patients will be treated at the MTD.

Dosing will be each night at approximately the same time. Pomalidomide should be taken with a glass of water on an empty stomach. **Only enough pomalidomide for one cycle of therapy will be supplied to the patient each cycle.**

Patients will continue receiving treatment with pomalidomide until disease progression or unacceptable toxicity develops.

Patients are to receive oral aspirin (325mg) as prophylactic anti-thrombotic treatment unless it is contraindicated, or the patient has a platelet count of less than 50,000. If the patient is intolerant of aspirin and has a platelet count of 50,000 or greater, the investigator is to prescribe therapeutic dose warfarin or low molecular weight heparin.

Pomalidomide capsules should be swallowed whole, and should not be broken, chewed or opened. Pomalidomide should be taken without food, at least 2 hours before or 2 hours after a meal.

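### Minor: the thrombocytopenia row of Table 3 sets the last dosing day by earlier dose reduction, where section 6.4.5 and Table 2 set it by schedule

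*Combined protocol and SAP*

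**What the plan says.** Section 6.4.5 gives a general rule for holds within a cycle: "For treatment interruptions during a cycle, the (28- or 21-day) schedule of each cycle will continue to be followed". Table 2 in the same section steps the dose down from 4 to 3, 2, 1 and 0.5 mg. Both of its column headings carry the qualifier "mg/dose/d 1-28 or d 1-21 depending on Schedule", so a reduction changes the milligrams and leaves the dosing days alone. Section 6.4.5 adds: "Once a dose has been reduced, it cannot be re-escalated".

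Table 3 covers cycle 2 onwards. Its thrombocytopenia row, for Grade 3 or 4 events on Days 2 to 14, has the drug held and blood counts followed weekly. On recovery to Grade 2 or better, the instruction is "restart at next lower dose level and continue the cycle until Day 28 or Day 21 if previously reduced". The neutropenia row for the same days has no condition about earlier reductions; it simply runs to the end of the cycle.

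Section 6.4.2 defines the alternative schedule: "With schedule B, patients will be treated for 21 days within each 28 day cycle". It is a switch for the whole trial, not a step for one patient: "Schedule B will only be explored if the MTD is exceeded at dose level 1 within Schedule A".

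**The concern.** The row uses a different criterion from the rest of the section. It decides between Day 28 and Day 21 by whether the dose was reduced before, while the general rule and Table 2 decide it by the patient's schedule. Nothing in the protocol moves an individual patient from 28 to 21 dosing days, and Schedule B is nowhere called a reduction.

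Followed literally, the row would give a Schedule B patient who has just recovered from severe thrombocytopenia drug in the week meant for rest. Schedule B exists only because 28-day dosing proved intolerable, so this is the wrong direction in which to err. Even if no one follows it literally, staff have two conflicting last dosing days for the same event.

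**Working it through.** The plan states no figure to reproduce. The check sets the two rules side by side, counts doses, and bounds how often the conflict could arise.

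**The two rules compared** (Grade 3 or 4 thrombocytopenia, Days 2 to 14, cycle 2 or later, restart after recovery)

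| Patient | Last day by Table 3 row | Last day by schedule (6.4.5, Table 2) | Difference |
|---|---|---|---|
| A, not previously reduced | 28 | 28 | none |
| A, previously reduced | 21 | 28 | up to 7 doses fewer |
| B, not previously reduced | 28 | 21 | up to 7 doses more |
| B, previously reduced | 21 | 21 | none |

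**Doses in the affected cycle.** From restart on day d, doses to Day 21 = max(0, 22 − d) and doses to Day 28 = 29 − d.

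- d = 9: 13 against 20. The Schedule B patient gets 7/13 = 54% more; the Schedule A patient gets 7/20 = 35% fewer.
- d = 15: 7 against 14. The changes are +100% and −50%.

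**Milligrams.** An unreduced Schedule B patient on 1 to 4 mg restarts at 0.5 to 3 mg (Table 2), so the excess is at most 7 × 0.5 = 3.5 mg to 7 × 3 = 21 mg. A previously reduced Schedule A patient who still has a lower level available takes 1 to 3 mg and restarts at 0.5 to 2 mg, so the shortfall is at most 3.5 to 14 mg.

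**Repetition and timing.** The excess can occur in one cycle at most. The row itself reduces the dose, reductions are permanent, and the patient then counts as previously reduced. The first rest-week dose falls on Day 22, at least 22 − 14 = 8 days after onset.

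**How often: any affected patient.** The only Grade 3/4 thrombocytopenia rate in the documents is 2 of 60, from the phase II study of pomalidomide plus dexamethasone in myeloma (section 4.2). That is 3.3%, exact 95% CI 0.41% to 11.53%. Assuming it carries over to the 30-patient maximum in section 6.4.1, 30 × 0.0333 = 1.0 patient (0.12 to 3.46), in any cycle and on any day.

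**How often: Schedule B.** Let p be the true DLT probability at dose level 1 of Schedule A. With full cohorts of 3, Schedule B opens if

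- 2 or more of the first 3 have a DLT: P1 = 3p²(1 − p) + p³, leaving at most 27 patients for B; or
- exactly 1 of the first 3 does and at least 1 of the next 3 does: P2 = 3p(1 − p)² × [1 − (1 − p)³], leaving at most 24.

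The values of p below are assumptions; the plan gives none.

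| p | P1 | P2 | B opens | Max. expected B patients, 27·P1 + 24·P2 | × 0.0333 | × 0.1153 |
|---|---|---|---|---|---|---|
| 10% | 0.028 | 0.066 | 9% | 2.34 | 0.08 | 0.27 |
| 20% | 0.104 | 0.187 | 29% | 7.31 | 0.24 | 0.84 |
| 30% | 0.216 | 0.290 | 51% | 12.79 | 0.43 | 1.47 |

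The last two columns are expected Schedule B patients with any Grade 3/4 thrombocytopenia, at the point estimate and at the upper confidence limit. Requiring cycle 2 or later, onset on Days 2 to 14, recovery and no earlier reduction lowers them further.

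**The case against.** The best defence is that the general rule in 6.4.5 already settles the matter. Section 6.4.2 fixes Schedule B at 21 days, Table 3 is presented as examples, and a reader with all of this in hand would stop a Schedule B patient at Day 21. That is probably what a careful site would do. But 6.4.5 also directs that reductions follow Table 3, so the row is operative, and a specific row is easily taken to override a general sentence.

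Two kinder readings are possible. One takes earlier reduction to mean being on the 21-day schedule, which makes all four situations come out right. No text supports it: in 6.4.5 the word refers to dose. The other takes continuing the cycle to Day 28 as calendar time and not dosing. The contrast with Day 21 makes sense only for dosing days.

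Discretion helps in one direction only. "The investigator may choose to modify pomalidomide dosing further downward" can excuse the early stop on Schedule A, which may even have been intended. On Schedule B it permits stopping at Day 21 but does not require it.

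It is also fair to ask why the neutropenia row is left alone. Its end-of-cycle wording is loose, but it introduces no rival criterion, so the general rule can govern it.

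The points about size stand. The borrowed rate counts patients, not events, and comes from another disease with dexamethasone. This trial admits platelet counts down to 20 K/µL when marrow infiltration is at least 60% (6.2.1, 6.2.2), and the rate may not apply to such patients. The frequency figures are therefore a rough guide. As to safeguards, weekly counts are stated for the hold; the row does not say they continue after restart.

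**Conclusion.** The row is wrong as written, and the matter is minor. It gives the wrong last dosing day for unreduced Schedule B patients. It also conflicts with 6.4.5 for previously reduced Schedule A patients, where the departure is cautious and arguably allowed.

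Recovery to Grade 2 or better and restart at a lower dose limit the risk. On the point estimate for thrombocytopenia, fewer than half a Schedule B patient is expected to have a qualifying grade of event at all. At the upper confidence limit with a 30% DLT rate, the figure is about 1.5 before the remaining conditions. These figures rest on the assumed DLT rates and on the myeloma rate carrying over. The textual conflict rests on neither. Because Table 3 starts at cycle 2 and DLTs are counted in cycle 1, the MTD determination is unaffected, and no endpoint is touched.

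**What to change.** In the Days 2 to 14 part of the thrombocytopenia row, replace the end-of-dosing condition with: until Day 28 (Schedule A) or Day 21 (Schedule B). If a shorter course after an earlier reduction was meant for Schedule A, state it as an explicit exception to the general rule in 6.4.5. The neutropenia row can stay as it is.

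The cost is a wording correction in one table cell. It needs no extra data, visits or analysis.
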